All patients fulfilling inclusion criteria will be referred for PET/CT scanning as arranged by the coordinating investigator. Patients will first undergo [¹⁸F] FDG PET as part of pre-treatment workup, followed by [⁶⁸ Ga] FAPI PET/CT within approximately seven days.

Imaging procedures are as follows:

[¹⁸F] FDG PET: PET/CT imaging will be conducted after >6 hours of fasting and among patients with normal blood glucose levels. The dose of [¹⁸F] FDG is calculated according to the patient’s weight, 3.7MBq/kg. Static PET/CT imaging will be performed using the Siemens PET/CT scanner 60 minutes after intravenous injection and will include the skull base to upper thighs.

[⁶⁸ Ga] FAPI PET/CT: No specific preparation is required for [⁶⁸ Ga] FAPI PET/CT. The specific radioisotope used is the [⁶⁸ Ga]-FAPI-46 variant, and the dose is calculated according to the patient’s weight, 1.8–2.2 MBq/kg. Static PET/CT imaging will be performed using the Siemens PET/CT

scanner 60 minutes after intravenous injection and includes the base of the skull to the upper thighs.

b. Chemotherapy Protocol

Patients will receive four cycles of FOLFIRINOX within approximately seven days of completing both PET/CT scans at the PAH medical oncology unit. The FOLFIRINOX regimen is defined as follows:

Day 1 Oxaliplatin 70mg/m² IV over two hours
Irinotecan 150mg/ m² IV over 90 mins
Leucovorin 300mg/m² IV over 90mins
Flurouracil 300mg/m² IV bolus
Followed by
Days 1–2 Flurouracil 2.4g/m² IV continuous infusion over 46 hours
Repeat cycle every two weeks for 4 cycles

Approximately 28 days after the patient has completed their fourth cycle of chemotherapy, patients will repeat a [¹⁸F] FDG PET/diagnostic CT chest, abdomen and pelvis as part of their standard of care imaging, followed by a [⁶⁸ Ga] FAPI PET/CT within approximately 7 days.

c. Histological Analysis

After diagnostic requirements have been completed, pre-treatment biopsy specimens will undergo FAP immunohistochemistry (IHC). Tissue samples will be acquired from Queensland Pathology at PAH laboratory. FFPE blocks or slides will be transferred to Translational Research Institute (TRI) histology core facility for staining and analysis. Tissue samples will be stored in secure PC2 laboratory.

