Participant imaging results reported by the nuclear medicine clinicians will be stored in computer files under password protection on secure servers. Only investigators in the research team have access to these files.

Clinical data will be recorded onto an electronic data capture system in a password-secured, firewall-protected network within Metro South Health. Only investigators in the research team have access to this, and all access will be audited by the Coordinating Principal Investigator.

Medical information or records in paper copies will be securely stored in locked facilities. All study-related documents and data collection forms will be archived in a secure environment for a minimum of 15 years. After this time, study data will be destroyed according to institutional policies.

9. Participant Safety/Risk Management

Additional procedures that a participant would receive in this study are [⁶⁸Ga] FAPI PET/CT scans pre- and post-chemotherapy.

a. Generic Risks

The risks and complications of the PET/CT procedure can include the following:

- Minor pain, discomfort and bruising as a result of the insertion of an intravenous cannula
- Physical discomfort related to positioning for the PET-CT scan
- A small amount of radiation to produce the PET images (details below)
- Infection from intravenous cannula site, which may require treatment with antibiotics
- An allergic reaction to injected tracer requiring further treatment.
- Death resulting from this procedure has not been reported

b. Risks Associated with Radiation Exposure

The dose of radiation a patient receives from a [¹⁸F] FAPI PET/CT at the PAH is approx. 10 millisieverts (mSv) and from [⁶⁸Ga] FAPI PET/CT is approx. 6.5mSv. The participants in this study will receive two [¹⁸F] FDG PET/CT scans, which is part of their standard of care therapy, and two [⁶⁸Ga] FAPI PET/CT scans. This equates to 23 mSv in total.

The annual occupational radiation exposure limit is 50 mSv per year, and even at this level, the increased cancer risk is so low that it cannot be measured against the normal incidence of cancer. It is, therefore, anticipated that participants will be at no increased risk of harmful effects from the PET/CT scans they receive.

c. Risks Associated with Injection of FAPI Ligand

Variations of the FAPI ligand, including [⁶⁸Ga]-FAPI-46, have been used in several human clinical trials to date. No adverse effects from an intravenous injection of radio-labelled FAPI have been identified.

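### The stated total radiation exposure of 23 mSv does not follow from the protocol's own per-scan figures, which sum to 33 mSv

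*Protocol*

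**What the plan says.** Protocol section 9b, on radiation risk, gives a dose for each type of scan. The first is printed as an 18F scan with the words "FAPI PET/CT at the PAH is approx. 10 millisieverts (mSv) and from", and the second, for 68Ga, reads "FAPI PET/CT is approx. 6.5mSv". The next sentence says that participants receive two "FDG PET/CT scans, which is part of their standard of care therapy, and two" 68Ga FAPI scans. The paragraph then closes the sum: "This equates to 23 mSv in total".

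The following paragraph supplies the yardstick, "The annual occupational radiation exposure limit is 50 mSv per year", and infers that no increased risk of harm is expected.

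Two other places fix the number of scans. The opening of section 9 names the procedures added by the study as "FAPI PET/CT scans pre- and post-chemotherapy". Section 6a schedules one FDG and one FAPI scan before treatment. Section 6b schedules a repeat "FDG PET/diagnostic CT chest, abdomen and pelvis as part of their standard of care imaging, followed by a" second FAPI scan after the fourth chemotherapy cycle.

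**The concern.** The total does not equal the sum of the components printed just before it. One of those components is also attached to a tracer and isotope combination (18F with FAPI) that appears nowhere in the imaging schedule.

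This is the protocol's only numerical statement of the participants' radiation exposure, and the risk conclusion is drawn from it. An understated total makes the comparison with 50 mSv look more favourable than the protocol's own inputs allow. Section 9d says that potential risks are set out in the participant information and consent forms, so the same figure may have been carried further. Those forms are not available here, and whether they repeat it is unknown.

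**Working it through.** **Inputs, all from the protocol**

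| Input | Value | Source |
|---|---|---|
| Dose per 18F scan (labelled FAPI, read as FDG) | about 10 mSv | 9b |
| Dose per 68Ga FAPI scan | about 6.5 mSv | 9b |
| FDG scans per participant | 2 | 9b; confirmed by 6a and 6b |
| FAPI scans per participant | 2 | 9 and 9b; confirmed by 6a and 6b |
| Stated total | 23 mSv | 9b |
| Comparator | 50 mSv per year | 9b |

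**Attempt to reproduce the stated figure.** Total = (FDG scans × 10) + (FAPI scans × 6.5).

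- Two FDG and two FAPI, as described: 20 + 13 = 33 mSv.
- No FDG and two FAPI, the study-added scans only: 13 mSv.
- One FDG and two FAPI: 10 + 13 = 23 mSv.

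Of all combinations of zero to two scans of each type, only the last gives 23, and it leaves out an FDG scan that the preceding sentence counts.

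**Could rounding explain it?** The doses are approximate. Assume, for illustration, 9.5–10.5 mSv for the FDG scan and 6.25–6.75 mSv for the FAPI scan:

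- lower end: 2 × 9.5 + 2 × 6.25 = 31.5 mSv
- upper end: 2 × 10.5 + 2 × 6.75 = 34.5 mSv

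To reach 23 mSv with four scans, the FDG dose would have to be (23 − 13)/2 = 5 mSv, or the FAPI dose (23 − 20)/2 = 1.5 mSv. Neither is a rounding of the printed value.

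**Size of the gap**

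- Difference: 33 − 23 = 10 mSv.
- Relative to the stated figure: 33/23 = 1.43, so the sum is 43% higher. Equivalently, the stated figure is 10/33 = 30% below the sum.
- Against the comparator: 33/50 = 66%, where the stated total gives 23/50 = 46%.

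**Do all four scans belong in one annual comparison?** Four two-weekly cycles, about 28 days to the repeat imaging, and intervals of about a week around the scans put all four within roughly three to four months. The full sum therefore falls within one year.

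**The case against.** The error itself is hard to dispute, but several points limit what may be drawn from it.

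- **The protocol shows a contradiction, not which number is wrong.** One component is visibly mislabelled, so reading the 10 mSv as the FDG dose is an inference. This stands as a caution. It does not rescue 23: FDG is the only 18F scan in the study, and if the label were taken literally no FDG dose would be given and no total could be formed.
- **The cause is unknown.** A dropped FDG scan gives exactly 23, but a one-digit typing slip would serve equally well. This stands, and the finding does not depend on the cause.
- **The benchmark is not crossed.** Both 23 and 33 mSv lie below 50 mSv. This also stands: the correction does not by itself overturn the risk conclusion on the protocol's own yardstick.
- **The study-attributable dose is not understated.** FDG is described as standard of care, and the FAPI scans add 13 mSv, which is less than the printed total. That is correct, but the text presents a total straight after listing all four scans, so the figure must be judged as a total.
- **Reliance by others is unproven.** The consent material and any radiation-safety submission are not available, so a correction there is needed only if they quote the figure.

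No endpoint, eligibility rule or analysis depends on this number. It still has to be corrected, because it is a wrong figure in a participant-risk statement and errs towards reassurance.

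**Conclusion.** The concern holds. On the protocol's own inputs the total is 33 mSv, and the stated 23 mSv is 10 mSv too low. Neither rounding nor a study-only reading accounts for the difference. The label on the 10 mSv figure is a second error in the same paragraph.

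The result rests on two readings: that the 10 mSv belongs to the FDG scan, and that each participant has two scans of each type, which the schedule confirms. It is the sum of the printed figures and not necessarily the full imaging dose. The repeat FDG scan is combined with a diagnostic CT of chest, abdomen and pelvis, and the protocol does not say whether the 10 mSv includes it.

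This must be fixed, although the sum stays below the protocol's own comparator.

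**What to change.** - Reconcile the per-scan doses, the scan count and the total in section 9b. As printed, the components give 33 mSv; if the sponsor finds that a component is wrong instead, correct it and recompute the total.
- Correct the 18F FAPI label to the scan that is meant.
- Show the two parts separately: on the present figures, 20 mSv from standard-of-care FDG scans and 13 mSv added by the study.
- State whether the 10 mSv covers the diagnostic CT done with the repeat FDG scan.
- Re-check the risk sentence and the comparison with 50 mSv against the reconciled total.
- Carry the same figure into any participant information or radiation-safety document that quotes 23 mSv.

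The cost is a wording correction and, presumably, a notification to the ethics committee. No procedure, schedule or analysis changes. The only drawback for the sponsor is that, on the present components, the stated exposure becomes less favourable.
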